**5.0 Grouping Factor:**

None

**6.0 Registration/Randomization Procedures**

## 6.1 Registration Procedures

6.11 To register a patient, access the Mayo Clinic Cancer Center (MCCC) web page and enter the registration/randomization application. The registration/randomization application is available 24 hours a day, 7 days a week. Back up and/or system support contact information is available on the Web site. If unable to access the Web site, call the MCCC Registration Office at [contact] between the hours of 8 a.m. and 4:30 p.m. Central Time (Monday through Friday).

The instructions for the registration/randomization application are available on the MCCC web page (<http://ccswww.mayo.edu/training/>) and detail the process for completing and confirming patient registration. Prior to initiation of protocol treatment, this process must be completed in its entirety and a MCCC subject ID number must be available as noted in the instructions. It is the responsibility of the individual and institution registering the patient to confirm the process has been successfully completed prior to release of the study agent. Patient registration via the registration/randomization application can be confirmed in any of the following ways:

- Contact the MCCC Registration Office [contact]. If the patient was fully registered, the MCCC Registration Office staff can access the information from the centralized database and confirm the registration.
- Refer to “Instructions for Remote Registration” in section “Finding/Displaying Information about A Registered Subject.”

6.12 Prior to accepting the registration, registration/randomization application will verify the following:

- IRB approval at the registering institution
- Patient eligibility
- Existence of a signed consent form
- Existence of a signed authorization for use and disclosure of protected health information

6.13 Documentation of IRB approval must be on file in the Registration Office before an investigator may register any patients.

In addition to submitting initial IRB approval documents, ongoing IRB approval documentation must be on file (no less than annually) at the Registration Office ([contact]). If the necessary documentation is not submitted in advance of attempting patient registration, the registration will not be accepted and the patient may not be enrolled in the protocol until the situation is resolved.

When the study has been permanently closed to patient enrollment, submission of annual IRB approvals to the Registration Office is no longer necessary.

- 6.14 Treatment on this protocol must commence at Mayo Clinic under the supervision of a medical oncologist/hematologist.
- 6.15 Treatment cannot begin prior to registration and must begin  $\leq$  28 days after registration.
- 6.16 Pretreatment tests/procedures (see Section 4.0) must be completed within the guidelines specified on the test schedule.
- 6.17 All required baseline symptoms (see Section 10.6) must be documented and graded.
- 6.18 Study drug is available on site.

## 7.0 Protocol Treatment

Daratumumab may be administered within  $\pm 1$  day of the scheduled dose if there are any logistical challenges (holiday, patient transport or other logistics, scheduling availability, etc.)

### 7.1 Treatment Schedule

#### 7.11 Consolidation 1 (Cycles 1-2 or 1-4, as the case may be for that patient)

Agent	Dose	Route	Day	Cycles
Daratumumab	16 mg/Kg* (IV) 1,800 mg (Injection)	IV or injection	1, 8, 15, 22	Cycle 1-2
Daratumumab	16 mg/Kg* (IV) 1,800 mg (injection)	IV or injection	1, 15	Cycle 3-4

Cycle 1 (to 3, as the case may be for that patient) length = 28 days;  
 Cycle 2 (or 4, as the case may be for that patient) length = up to 84 days (4 weeks treatment + window period up to 8 weeks between Consolidation 1 and ASCT)  
 Treatment Window (for patients receiving treatment through a local medical doctor)=  $\pm 5$  days

\*Any dose-adjustments will be made as per the prescriber information.

Daratumumab administration as per prescriber information and institutional guidelines.

#### 7.12 Consolidation 2 (Cycle 3 or 5, as the case may be for that patient)

- All patients enrolled in the trial after completing consolidation 1 treatment will proceed to a SCT with Day 0 of SCT within 8 weeks of completing cycle 2 (or 4, as the case may be for that patient), Day 28 of consolidation 1.
- Stem cell collection could have been completed prior to initiating consolidation 1 or may be performed within the up to 8-week period between completion of Cycle 2 (or 4, as the case may be for that patient), Day 28 and Day 0 of SCT.
- Consolidation 1 should not be interrupted for the purpose of stem cell collection.
- SCT procedures should be completed as per institutional standards.
- Consolidation 2 period will be considered up until the Day 100 visit ( $\pm 10$  days as per institutional BMT program scheduling).
- Cycle 3 (or 5, as the case may be for that patient) length = Up to 124 days (Day 100 visit of ASCT occurs 90-110 days after ASCT + window period up to 14 days between Day 100 visit and start of Maintenance)

#### 7.13 Maintenance (Cycles 4 and Beyond, or cycle 6 and beyond as the case may be for that patient)

- All patients will be initiated on maintenance therapy as below within 14 days of completing Day 100 visit post-SCT.

Agent	Dose	Route	Day	Cycles
Daratumumab	16 mg/Kg* (IV) 1,800 mg (Injection)	IV or Injection	1	Cycle 4-15 (or 6-17)
Lenalidomide	10 mg*	PO	1-21	Cycle 4-15

				(or 6-17)
--	--	--	--	-----------

Cycles 4-15 (or 6-17) length = 28 days

\*Any dose-adjustments will be made as per the prescriber information.

Daratumumab administrations as per prescriber information and institutional guidelines.

Note: Thromboprophylaxis is required as standard of care (see Section 9.3) for all patients on maintenance treatment.

- **NOTE:** Prior to Cycle 16 (or 18), patients who are still maintaining response will proceed to maintenance with single-agent daratumumab every 3 months till disease progression or unwanted adverse events, if any. Cycles 16 and beyond length = 90 days (3 months).
- In the event of disease progression, intolerable adverse event or patient refusal for continued therapy, they will proceed to event monitoring without any additional anti-MM therapy.
- Considering that there are newer immunotherapy compounds being made available for the treatment of multiple myeloma, based on the initial results of this clinical trial, amendments may be put in place to add more arms to the study with newer, proven safe combination regimens, especially for maintenance treatment.

#### 7.2 Treatment by a local medical doctor (LMD) allowed.

When it has been determined that a patient's malignant disease is stable and the patient is tolerating therapy without excessive toxicity at a stable dose level, the patient may continue treatment via the patient's Local Medical Doctor (LMD). The patient will be required to return to Mayo Clinic for all study visits.

#### 7.3 Overdose

Any dose of study drug in excess of that specified in this protocol is considered to be an overdose. Signs and symptoms of an overdose that meet any Serious Adverse Event criterion must be reported as a Serious Adverse Event in the appropriate time frame and documented as clinical sequelae to an overdose.

There has been no experience of overdosage with daratumumab in clinical studies. Doses up to 24 mg/kg have been administered intravenously in a clinical study without reaching the maximum tolerated dose. There is no known specific antidote for daratumumab overdose. In the event of an overdose, the subject should be monitored for any signs or symptoms of adverse effects and appropriate symptomatic treatment be instituted immediately.

Refer to Section 10 for further information regarding AE reporting.

### 8.0 Dosage Modification Based on Adverse Events

Any adverse event noted in the study and its resultant dose-modifications should be managed as per the prescribing information of daratumumab and/or lenalidomide as per which of these two drugs the adverse event is attributable to.

**ALERT:** **ADR reporting may be required for some adverse events (See Section 10)**

#### 8.1 General Considerations:

- Missed doses for lenalidomide are to be omitted rather than made up, unless the dose was forgotten and remembered on the same day, in which case the dose can be taken

that day. Any doses missed on a particular day are not to be made up the next day. Doses that are considered to be vomited are not to be made up and a mention about the time of dose and time of vomiting episode should be made in the pill diary.

- b) Daratumumab may be administered within  $\pm 1$  day of the scheduled dose if there are any logistical challenges (holiday, patient transport or other logistics, scheduling availability, etc.)
- c) If multiple toxicities are experienced, dose modifications will be based on the toxicity requiring the largest dose reduction.
- d) Reductions are based on the dose given in the preceding cycle and are based on toxicities with an attribution of possible, probable, or definite that were observed since the prior toxicity evaluation.
- e) If a drug is omitted due to specific adverse events and the patient is on combination therapy (maintenance therapy), the other agents, considered unrelated to the adverse event may be continued.
- f) If a patient cannot be administered a dose of daratumumab during Consolidation 1 (Cycles 1-2 or 1-4, as the case may be for that patient) for  $>28$  days due to adverse events or any other reason, the patient should be removed from the study treatment and go to event monitoring. (NOTE: Patients on maintenance therapy (cycles 4 and beyond, or cycle 6 and beyond as the case may be for that patient) may be continued on treatment with single-agent daratumumab or lenalidomide in case the other agent has to be permanently discontinued in absence of disease progression. If a patient on maintenance treatment must discontinue both, lenalidomide and daratumumab, they should be removed from the protocol therapy and proceed to event monitoring.

## 8.2 Lenalidomide Dose Modifications

Lenalidomide (Days 1-21)	
Starting dose	10mg
-1	5 mg
-2	Discontinue

→ → Use the NCI Common Terminology Criteria for Adverse Events (CTCAE) version 4.0\*  
unless otherwise specified ← ←

CTCAE System/Organ/Class (SOC)	ADVERSE EVENT	AGENT	ACTION**

CTCAE System/Organ/Class (SOC)	ADVERSE EVENT	AGENT	ACTION**
Investigations	Platelet count decreased Grade 4	Lenalidomide	
*Omit dose until AE has resolved to Grade 1 or better
 
 
• Follow CBC weekly
 
• If thrombocytopenia <math><30,000/\text{mm}^3</math> recurs, reduce dose by one dose level (by 5 mg) and continue therapy when platelet count <math>\geq 30,000/\text{mm}^3</math>
 
 
If, after lenalidomide has been omitted, and the AE does not return to <math>\leq</math>Grade 1 within 4 weeks, then the patient may continue on single-agent daratumumab till the completion of maintenance and then proceed to Event Monitoring

	Neutrophil count decreased Grade 4		
*Omit dose until AE has resolved to Grade 2 or better
 
 
• Follow CBC weekly
 
* If neutropenia has resolved to <math>\leq</math>Grade 2, resume dose at one level lower
 
* If, after lenalidomide has been omitted, and the AE does not return to <math>\leq</math>Grade 1 within 4 weeks, then the patient may continue on single-agent daratumumab till the completion of maintenance and then proceed to Event Monitoring
 

Blood and lymphatic system disorders	Anemia Grade 4		
*Omit dose until AE has resolved to Grade 2 or better
 
 
• Follow CBC weekly
 
* If anemia has resolved to <math>\leq</math>Grade 2, resume dose at one level lower
 
* If, after lenalidomide has been omitted, and the AE does not return to <math>\leq</math>Grade 1 within 4 weeks, then the patient may continue on single-agent daratumumab till the completion of maintenance and then proceed to Event Monitoring
 

	Febrile neutropenia $\geq$ Grade 3		
 
• Omit dose and follow CBC weekly
 
• If neutropenia has resolved to <math>\leq</math>Grade 2, resume dose at same level with GCSF support (See Section 9.6)
 

CTCAE System/Organ/Class (SOC)	ADVERSE EVENT	AGENT	ACTION**
Cardiac disorders	Sinus bradycardia/ other cardiac arrhythmia Grade 2	Lenalidomide	Omit dose and follow at least weekly until resolution • If AE resolves to $\leq$ Grade 1, reduce dose by one dose level (by 5mg) and continue therapy
	$\geq$ Grade 3		• Discontinue study treatment and go to event monitoring
Vascular disorders	Thromboembolic event $\geq$ Grade 3		• Omit dose and start anticoagulation; restart at investigator's discretion (maintain dose level)
Immune system disorders	Allergic reaction Grade 2-3		• Omit dose and follow at least weekly until resolution • If AE resolves to $\leq$ Grade 1, reduce dose by 5 mg and continue therapy
	Anaphylaxis Grade 4		• Discontinue study treatment and go to event monitoring
Skin and subcutaneous tissue disorders	Erythema multiforme $\geq$ Grade 3		Discontinue study treatment and go to event monitoring
	Skin ulceration $\geq$ Grade 2		Discontinue study treatment and go to event monitoring
	Other: Non-blistering rash Grade 3		• If Grade 3 omit dose and follow weekly until resolution • If AE resolves to $\leq$ Grade 2 continue therapy
	Other: Non-blistering rash Grade 4		• Discontinue study treatment and go to event monitoring
Other AEs	Non-hematologic AE assessed as related to lenalidomide $\geq$ Grade 3		• Omit dose and follow at least weekly until resolution • If the AE resolves to $\leq$ Grade 2, implement one dose reduction step and continue therapy (per Table 8.2)

\* Located at [http://ctep.cancer.gov/protocolDevelopment/electronic\\_applications.ctc.htm](http://ctep.cancer.gov/protocolDevelopment/electronic_applications.ctc.htm)

\*\* Use the following to describe actions in the Action column:

- Omit = The current dose(s) for the specified drug(s) during a cycle is skipped. The patient does not make up the omitted dose(s) at a later time
- Hold/Delay = The current dose(s) of all drugs during a cycle is delayed. The patient does make up the delayed dose(s) when the patient meets the protocol criteria to restart drugs.
- Discontinue = The specified drug(s) are totally stopped.

If lenalidomide has been omitted and the toxicity does not return to  $\leq$ Grade 2 within 28 days during Consolidation 1 (Cycles 1-2), may continue on single-agent daratumumab till the completion of maintenance and then proceed to Event Monitoring.

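### In Table 8.2, the Grade 4 neutrophil and anemia rows give two answers for a patient at Grade 2 at week 4: resume lenalidomide at a lower level, or go on with daratumumab alone

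*Combined protocol and SAP*

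**What the plan says.** The Grade 4 neutrophil row and the Grade 4 anemia row of the table in Section 8.2 each contain three instructions on lenalidomide:

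- Omission: "Omit dose until AE has resolved to Grade 2 or better".
- Restart, once the event is at or below "Grade 2, resume dose at one level lower".
- A time limit, for an event that has not come back to at or below "Grade 1 within 4 weeks, then the patient may continue on single-agent daratumumab till the completion of maintenance", followed by event monitoring.

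Four other places bear on the same decision:

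- Section 8.0 says that adverse events and the dose changes they lead to "should be managed as per the prescribing information of daratumumab and/or lenalidomide".
- Section 8.1(e) and (f) let a maintenance patient carry on with one drug when the other is omitted or permanently stopped. They set no recovery grade.
- The note closing Section 8.2 opens "If lenalidomide has been omitted and the toxicity does not return to" and goes on, after a less-than-or-equal sign, "Grade 2 within 28 days during Consolidation 1 (Cycles 1-2), may continue on single-agent daratumumab till the completion of maintenance".
- Section 13.3 lists an omission of daratumumab or lenalidomide running more than 28 days past the scheduled retreatment date among the reasons for leaving protocol treatment for event monitoring.

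**The concern.** These are the operative rules for restarting a myelosuppressive drug after a Grade 4 event. The restart sentence uses Grade 2 as its threshold and the time-limit sentence uses Grade 1. Two investigators who each follow the text exactly could treat the same patient differently, one resuming lenalidomide at a reduced level and the other leaving it off, and neither would have deviated from the protocol.

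What is at stake is how much lenalidomide is given in maintenance, and with it two secondary objectives: the safety profile of daratumumab with lenalidomide (2.24) and the MRD-negative rate after 1 year of the combination (2.21). If the regimen delivered depends on which sentence an investigator applied, those estimates describe a less well-defined treatment than the protocol intends.

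**Working it through.** No sample size, power or event count bears on this point, so the check is to read the rules side by side.

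**Step 1. Which rule applies at week 4, neutrophil and anemia rows.** The restart rule is met at Grade 2 or lower. The time-limit rule is met when the event is not at Grade 1 or lower.

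| State at week 4 | Restart rule met? | Time-limit rule met? |
|---|---|---|
| Resolved or Grade 1 | yes | no |
| Grade 2 | yes | yes |
| Grade 3 or 4 | no | yes |

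The overlap is Grade 2 and nothing else. It also reaches a patient who got to Grade 2 early and has already resumed: if that patient is still at Grade 2 at week 4, the time-limit sentence, read literally, still applies.

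**Step 2. Which rows are affected.** Three rows carry a 4-week rule: platelets, neutrophils and anemia. The platelet row says "Omit dose until AE has resolved to Grade 1 or better" and uses Grade 1 in its 4-week sentence too, so its thresholds agree. The febrile neutropenia row has no 4-week rule. The overlap is therefore in 2 of 3 rows.

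**Step 3. What differs for the patient.** The dose levels in 8.2 are 10 mg, then 5 mg, then discontinuation. For a patient at the 10 mg starting dose, one sentence leads to 5 mg and the other to no lenalidomide. For a patient already at 5 mg, one level lower is discontinuation, so the two sentences give the same lenalidomide dose. Daratumumab may continue under either.

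**Step 4. Does other text settle it?**

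- Section 8.0 points to the prescribing information, as does the footnote to the maintenance schedule in 7.13, while 8.2 sets out detailed rules of its own. No order of precedence is stated.
- Section 8.1(e) and (f) permit single-agent continuation but do not say at what grade lenalidomide must be given up.
- The closing note of 8.2 sets a Grade 2, 28-day rule for lenalidomide in Consolidation 1. The Consolidation 1 schedule in 7.11 lists only daratumumab, and lenalidomide first appears in 7.13 at Cycle 4 (or 6). The note governs a period in which the drug is not given.
- Section 13.3 adds a conflict. A lenalidomide omission beyond its 28-day limit takes the patient off protocol treatment, whereas 8.1 and the 8.2 rows allow daratumumab to continue. The clocks differ as well: 13.3 counts from the scheduled retreatment date, and 8.2 speaks only of 4 weeks after omission.

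**Step 5. Reach.** Under 7.13, maintenance begins after the Day 100 visit, and the primary endpoint is MRD status at that visit (16.11). The primary endpoint cannot be affected.

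**The case against.** The best defense is that the sentences in each row form a sequence. A patient who reaches Grade 2 resumes one level lower, and the last sentence is for a patient whose lenalidomide is still being withheld. That sentence is also permissive, since it says the patient may continue on daratumumab alone. Section 8.0 may settle the matter through the prescribing information, which is not available here. The outcomes involved are secondary and are estimated descriptively under 16.42.

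This softens the point but does not remove it. The sequential reading is plausible, yet on that reading the time limit would be expected to use the threshold of the restart sentence, and it uses a stricter one. The permissive wording comes with no criterion for choosing it over restarting, and no exemption for a patient who has resumed. Section 8.0 does not say whether it or the table prevails.

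Three stronger readings are tempting, and the documents do not support them:

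- **That the platelet row has the same fault.** A reader might set its Grade 1 requirement against the later instruction, for thrombocytopenia that recurs below 30,000/mm³, to "reduce dose by one dose level (by 5 mg) and continue therapy when platelet count" is at least 30,000/mm³. That instruction covers a different situation, a recurrence with a dose reduction, and a separate rule for it is not in itself a contradiction. The protocol does not reproduce the CTCAE platelet cut-offs, so the distance between the grade and the count cannot be judged from it.
- **That the closing note gives maintenance patients a third threshold.** Grade 2 is already in the neutrophil and anemia rows, and the note confines itself to Consolidation 1. Its defect is that it names a period without lenalidomide.
- **That the number of patients affected can be worked out from the 45 evaluable patients.** The documents give no rate of Grade 4 cytopenia in maintenance and no share of such patients who would be at Grade 2 at week 4. The 45 also counts everyone who began treatment, including those who never reach maintenance.

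**Conclusion.** The neutrophil and anemia rows contradict themselves at Grade 2 at week 4, and nothing in 8.0, 8.1 or 13.3 resolves it. This is an internal inconsistency in the text, not a criticism of either threshold. The closing note of 8.2, the 28-day rule in 13.3 and the unranked deferral in 8.0 need reconciling with the table for related reasons.

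The consequence is confined to maintenance. On the dose levels in 8.2, lenalidomide exposure differs between the two sentences for a patient at the 10 mg starting dose. The safety profile (2.24) and the 1-year MRD rate (2.21) could shift, by an amount and in a number of patients that the documents leave unknown. The conclusion rests on reading the sentences as written, and on the prescribing information not having been given precedence anywhere in the protocol. It is worth correcting because the rules concern restarting treatment after a Grade 4 event.

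**What to change.** The sponsor should:

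- reconcile the restart sentence and the 4-week sentence in the neutrophil and anemia rows of 8.2, so that a patient at Grade 2 at week 4 falls under one instruction, and make clear what applies to a patient who has already resumed;
- reconcile the closing note of 8.2 with the Consolidation 1 schedule in 7.11;
- reconcile the lenalidomide part of the 28-day criterion in 13.3 with the single-agent continuation allowed in 8.1 and 8.2;
- state whether the table in 8.2 or the prescribing information prevails where they differ.

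Which threshold applies, and how the rule is built, is the sponsor's clinical decision. The cost is amendment wording only. Sample size, the decision rule and the primary analysis do not change.

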##### 15.22 Formulation and Dispensing:

Commercially available for oral administration as: Capsules: 5 mg, 10 mg, 15 mg and 25 mg

Lenalidomide is approved for marketing only under a FDA approved, restricted distribution program called Revlimid REMS. Physicians, pharmacies, and patients must be registered; a maximum 28-day supply may be dispensed; a new

prescription is required each time it is filled; pregnancy testing is required for females of childbearing potential.

15.23 **Preparation, storage, and stability:** Store oral capsules at controlled room temperature between 15°C and 30°C (59 °F and 86 °F). Refer to labeling on the bottle for expiration date of the commercial tablets.

15.24 **Administration:** Refer to the treatment section for specific administration instructions. Administer with water. Swallow capsule whole; do not break, open, or chew.

15.25 **Pharmacokinetic information:**  
**Absorption:** Rapid  
**Metabolism:** Approximately two-thirds of Lenalidomide is eliminated unchanged through urinary excretion.  
**Protein binding:** ~30%  
**Time to peak, plasma:** Healthy volunteers: 0.6-1.5 hours; Myeloma patients: 0.5-4 hours  
**Half-life elimination:** ~3 hours  
**Excretion:** Urine (~67% as unchanged drug)

15.26 **Potential Drug Interactions:**  
**Increased Effect/Toxicity:** Abatacept and Anakinra may increase the risk of serious infection when used in combination with Lenalidomide. Lenalidomide may increase the risk of infections associated with vaccines (live organism).  
**Decreased Effect:** Lenalidomide may decrease the effect of vaccines (dead organisms).  
**Herb/Nutraceutical Interactions:** Avoid echinacea (has immunostimulant properties; consider therapy modifications).

15.27 **Known potential adverse events:** Consult the package insert for the most current and complete information.

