**Rare known potential toxicities, <1% (Limited to important or life-threatening):**

Angioedema, Stevens-Johnson Syndrome and Toxic Epidermal Necrolysis

Tumor Lysis Syndrome

15.28 **Drug procurement:** As a requirement of the REMS program, access to Lenalidomide is restricted. Lenalidomide is approved for marketing only under a FDA approved, restricted distribution program called REVCLIMID REMS ([www.REVCLIMIDREMS.com](http://www.REVCLIMIDREMS.com)) formerly known as the RevAssist program. Physicians, pharmacies, and patients must be registered; a maximum 28-day supply may be dispensed; a new prescription is required each time it is filled; pregnancy testing is required for females of childbearing potential.

15.29 **Nursing Guidelines:**

- Myelosuppression is dose-dependent and reversible with treatment interruption and/or dose reduction. Monitor CBC w/diff regularly. Instruct patient to report any unusual bruising or bleeding (thrombocytopenia); signs and symptoms of infection (neutropenia); and energy conserving lifestyle (anemia).
- Lenalidomide can have thrombotic adverse events (i.e DVT and PE). Instruct patient to report any limb swelling or pain, and to seek medical attention for shortness of breath or chest pain.
- Because of the potential for birth defects patients should be instructed in effective methods of birth control. Female patients should use 2 forms of birth control during treatment and for 4 weeks after discontinuing therapy. Males must be instructed to use a latex condom during any sexual contact with a woman of child bearing potential (even if they have had a vasectomy), because it is unknown if lenalidomide is present in semen.
- Patients may experience pruritus, rash and dry skin. Because of the rare risk of Steven's Johnson Syndrome, patients should immediately report any rash to their provider.
- Drug may cause hyperglycemia. Patients with diabetes or impaired fasting glucose may need to have their glucose levels monitored more closely.

- Gastrointestinal side effects (diarrhea, constipation, nausea, dyspepsia, anorexia, etc) are commonly seen. Manage patient symptomatically and monitor for effectiveness.
- Patients may experience myalgias, arthralgias, and other generalized pain. Administer analgesics as ordered and monitor for their effectiveness.
- Upper respiratory symptoms (nasopharyngitis, cough, epistaxis, etc.) can be seen. Manage symptomatically and monitor for effectiveness.

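### Table 8.2 has no row for Stevens-Johnson syndrome, toxic epidermal necrolysis or blistering rash, so its catch-all row, applied as written, would restart lenalidomide at 5 mg

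*Combined protocol and SAP*

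**What the plan says.** Section 15.27 (known lenalidomide toxicities) carries the subheading "Rare known potential toxicities, <1% (Limited to important or life-threatening"), and its first entry is "Angioedema, Stevens-Johnson Syndrome and Toxic Epidermal Necrolysis". The nursing guidelines in 15.29 ask patients to report a rash at once because of SJS, but give no dosing action.

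Section 8.2 sets a lenalidomide ladder of 10 mg, then 5 mg (level -1), then discontinuation (level -2). The skin block of Table 8.2 has four entries: erythema multiforme of Grade 3 or higher, skin ulceration of Grade 2 or higher, non-blistering rash of Grade 3, and "Other: Non-blistering rash Grade 4". For all but the Grade 3 rash, the action is "Discontinue study treatment and go to event monitoring".

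The last row, Other AEs, covers any "Non-hematologic AE assessed as related to lenalidomide" of Grade 3 or higher. The site omits the dose, follows the patient at least weekly and, once the event is at Grade 2 or lower, is to "implement one dose reduction step and continue therapy (per Table 8.2").

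Several provisions outside the table also bear on the point:
- Section 8.0 and the footnote to the 7.13 dosing table refer dose changes to the prescribing information. Section 15.27 says "Consult the package insert for the most current and complete information".
- Section 7.13 moves a patient with an intolerable adverse event to event monitoring. Section 13.1 makes continued treatment depend on there being no unacceptable toxicity.
- Section 8.1(c) applies the largest reduction when several toxicities occur together.
- Section 13.3 ends treatment on the investigator's judgement, or when either drug is omitted for more than 28 days past the due date.

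**The concern.** The protocol recognises SJS and TEN as serious lenalidomide risks but gives no dosing action specific to them. Its rash rows are limited to non-blistering rash, with no blistering counterpart. What remains is a catch-all row with no upper grade limit and no exclusions, and that row ends in a restart. On its face, the table treats SJS or TEN more leniently than a severe rash without blisters.

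What is at stake is patient safety in a rare event. A site that goes straight to the table would re-expose a patient to lenalidomide after a reaction that the protocol itself classes as important or life-threatening. A site that starts from 8.0 might act differently. Section 7.2 lets a local doctor give treatment once the patient is stable, which adds to the value of a table that can be followed without cross-reading.

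**Working it through.** The plan states no figure on this point. The check is a reading of the table, followed by a simple ceiling on the number of cases.

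**1. Which row applies.** Take a lenalidomide-related case of SJS or TEN of Grade 3 or higher during maintenance, not also coded as a listed skin event.

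| Event | Action in Table 8.2 |
|---|---|
| Erythema multiforme, Grade 3 or higher | Stop study treatment |
| Skin ulceration, Grade 2 or higher | Stop study treatment |
| Non-blistering rash, Grade 4 | Stop study treatment |
| Non-blistering rash, Grade 3 | Omit, continue at Grade 2 or lower |
| SJS, TEN, blistering or exfoliative rash | No row; falls to Other AEs |
| Other AEs, Grade 3 or higher | Omit, then one step down and continue at Grade 2 or lower |

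**2. What the ladder then does.** From 10 mg, one step down is 5 mg, so lenalidomide restarts. From 5 mg, one step down is level -2, so lenalidomide stops. The restart path therefore exists only for a patient still on 10 mg.

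**3. What narrows it.**
- Section 8.1(c) leads to a stop if the event is also coded as erythema multiforme or skin ulceration at the listed grades. It ranks toxicities and does not rank the table against the prescribing information.
- The 28-day clause in 13.3 leads off treatment if recovery takes longer. The 28-day sentence that closes Table 8.2 does not help, because it refers to Consolidation 1, when only daratumumab is given.
- The stops in 7.13 (intolerable event), 13.1 (unacceptable toxicity) and 13.3 (investigator's opinion) all depend on judgement. None names SJS or TEN.
- Sections 8.0 and 7.13 point to the prescribing information without mentioning Table 8.2 or saying which governs if they differ.

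A restart therefore needs all of the following: a 10 mg patient, an event not coded under a listed skin row, recovery to Grade 2 or lower within the 28-day limit, an investigator who does not invoke a judgement-based stop, and a site that follows the table instead of 8.0.

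**4. Ceiling on cases of any kind.** Inputs: 45 evaluable and 50 registered patients (16.12), and the <1% frequency (15.27). Expected ceiling = n × p.
- If <1% is taken as the combined SJS/TEN rate: 45 × 0.01 = 0.45 and 50 × 0.01 = 0.50.
- If <1% applies to each term (combined below 2%): 45 × 0.02 = 0.90 and 50 × 0.02 = 1.00.

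Both overstate exposure. Five of the 50 are an allowance for ineligibility, cancellation, violation or other reasons, and lenalidomide starts only after the Day 100 visit. Cases that would reach a restart are fewer still and cannot be estimated from the documents.

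**5. Effect on the analysis.** The primary endpoint is read at the Day 100 visit, before lenalidomide begins. Sample size, significance level and power do not depend on this row.

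**The case against.** The strongest reply is that 8.0 opens the whole dose-modification section without qualification and sends adverse-event management to the prescribing information, while the 7.13 footnote is attached to the lenalidomide dose itself. On that reading the table is never meant to be used alone. The judgement-based stops add further protection. This largely stands: it makes an actual restart unlikely and keeps the point at the level of a clarification. It does not remove the explicit action in the Other AEs row, and no sentence subordinates that row to the prescribing information.

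A reader might go further and infer that the protocol instructs rechallenge after SJS or TEN, or that it contradicts the label. The documents support neither. The provisions above point away from rechallenge, and the prescribing information is not reproduced, so no conflict can be shown. The CTCAE text is also absent, so how these events are graded as they recover, and whether a Grade 2 state is defined for them, is an assumption in the restart path.

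It can also be said that other rare events on the same list, such as tumor lysis syndrome, have no row of their own, and that a catch-all plus the label is an acceptable drafting choice for commercial drugs. That is fair in general. The difference here is that neighbouring rows in the same skin block already stop treatment for related severe events, so the catch-all produces an inconsistency within the table.

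**Conclusion.** The point holds as a rare-event safety correction of low priority: a change the sponsor could make. Table 8.2 omits SJS, TEN and blistering or exfoliative rash. Applied as written, its catch-all row would restart a 10 mg patient at 5 mg after recovery to Grade 2 or lower, while the table stops treatment for three neighbouring severe skin events. An actual restart is unlikely given 8.0, 7.13, 8.1(c), 13.1 and 13.3.

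The ceiling is about 0.5 to 1 expected case of any kind, assuming that the <1% in 15.27 is either a combined or a per-term rate. The restart subset is smaller and unquantified. There is no effect on sample size or error rates. The conclusion rests on the protocol's own text and on no claim about the content of the label.

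**What to change.** Add one row to the skin block of Table 8.2: *SJS, TEN, or blistering/exfoliative rash suspected to be either: permanently discontinue lenalidomide, no rechallenge.* Exclude these events from the Other AEs row.

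State in the new row what happens to daratumumab. One option is that it may continue as a single agent under 8.1(e)-(f) if judged unrelated, which fits the note in 8.3 that modifies daratumumab only when the event cannot be ascribed to lenalidomide or another concurrent drug. In that case the row should also say that the 28-day clause in 13.3 does not end daratumumab. The other option is that all study treatment stops, as in the neighbouring discontinuation rows. Either closes the gap; the sponsor should choose one.

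A blanket sentence in 8.0 making the stricter of table and prescribing information prevail is not recommended. It would reach every row, including the cytopenias that 15.27 lists as common (>10%), and it would leave open what counts as stricter.

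The cost is one row and one exclusion in an amendment; the document history lists Amendment 9 as pending. The downside is that a rare patient, at most about 0.5 to 1 expected, stops lenalidomide permanently.
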